6.2 Study Population

6.2.1 Approximate Number of Subjects

Approximately 126 Geisinger subjects will participate in this study (63 in each study arm).

6.2.2 Inclusion Criteria

- Inclusion criteria include:
 - Able and willing to provide written informed consent
 - Ages 18 to 64 years (inclusive)
 - Based on medical history (including available medical records), chronic low back pain must have been present for at least 3 months
 - Completed at least 4 weeks of non-surgical pain management and physical therapy with no apparent benefit
 - Has a mean NPRS pain score that is \geq to 4 (without rounding) over the 7-day screening period

- Subject has a score of 1-3 based on the American Society of Anesthesiologists Physical Status Classification System
- Agrees to comply with all study requirements throughout the entire study period

Exclusion Criteria

- *Exclusions based on potential medical or lifestyle confounders:*
 - Has a body mass index (BMI) > 40 kg/m²
 - Pain related to cancer, fibromyalgia, or disk herniation
 - History of a major psychiatric disorder not controlled with medication or has behavioral factors that would interfere with proper study procedures
 - Is not ambulatory/has significant motor impairment
 - Surgery in the past 3 months
 - Open workers compensation claim
 - Planning to have surgery in the next 3 months
 - Planning to start a new exercise program in the next 3 months
 - Planning to start a new treatment for their pain (e.g. medication, physiotherapy, acupuncture, electrical nerve stimulation) in the next 3 months
- *Exclusions based on potential drug-related cofounders:*
 - Current or recent history (in past year) of substance abuse disorder
 - Currently pregnant/breastfeeding or planning to in the next 3 months
 - Was administered an epidural steroid during the 3 months prior to screening
- *Exclusions based on ability to use EaseVR effectively:*
 - Comorbidities including neurological, psychosocial, sensory, or other disorders that may impact pain perception
 - Diagnosis of epilepsy, dementia, migraines, or other neurological disorders that may prevent VR usage, and/or other medical conditions predisposed to nausea and dizziness
 - Hypersensitivity to flashing lights or motion
 - Claustrophobia
 - Lack of stereoscopic vision
 - Severe hearing impairment
 - Injury to eyes, face, or neck that prevents comfortable VR usage
 - Planning to take a vacation from their home for more than one week in the next 8 weeks

6.3 Recruitment

The primary and collaborating investigator(s) will identify potential subjects in the Geisinger system who are scheduled for a clinic visit to address their chronic low back pain. These patients will be pre-screened via manual chart review of their electronic health record (EHR) by the research team. Patients meeting the inclusion/exclusion criteria will be called by an IRB-approved study team member (e.g. primary and collaborating physicians, research project coordinator, research assistant) approximately one week prior to their scheduled clinic visit. After hearing a description of the study and completing a short screening assessment, eligible

patients will be asked to report their average lower back pain over the last 24 hours via a Numeric Pain Rating Scale (NPRS) score for 7 days. Each subject will choose how they want to report their daily NPRS scores and will be given the following options: phone calls, texts, or web-based entry via REDCap. They will be instructed to record their scores at the same time each day (\pm 2 hours).

At the end of the 7-day screening period, the study team will assess daily NPRS scores to determine if the subject meets the pain eligibility requirements: (1) subjects must complete at least 5 of 7 daily NPRS scores in the previous 7-day screening period and (2) the overall average NPRS score must remain between 4 and 10 (inclusive) during the screening period. Subjects who are deemed eligible will be approached by a member of the study team during their clinic visit to provide more information about the study and administer informed consent for interested patients.

6.4 Study Duration

6.4.1 Approximate Duration of Subject Participation

Subjects will participate in the study for approximately 12 months. This includes the baseline visit, the 8 weeks completing the VR modules, the 4-week follow-up period, and the final retrospective data pull at 12 months.

6.4.2 Approximate Duration of Study

This study will be completed in approximately two years. The end of the study is the last visit of the last subject or end of collection of data from the patient's electronic health record.

6.5 Procedures

After informed consent, patients will be randomized by computer 1:1 to either the VR sham or EaseVRx group. Providers and patients will be blinded in regard to whether the patient will receive EaseVRx or the VR sham device. The headset will be provided by a study team member during the clinic visit, along with device paper education materials. The patients will be instructed to not use the device while ambulating. The EaseVRx and VR sham devices will be presented in the context of an alternate method of pain control to opioids or other pharmacology. The patients will be assured they may receive the standard of care (SOC) for pain control in addition to the device. SOC pain management will follow pre-established clinical guidelines, and the additional VR-based or sham device will be made available but with no restriction on the use of other pain management methods as desired by the subject and prescribed by his/her provider.

All research activities will be conducted remotely after the initial baseline study visit. Each subject will be asked to complete an 8-week program with assigned modules each week. Each week, subjects will be asked to complete 5 modules, averaging 6 minutes in duration and ranging from 2 to 16 minutes in duration. At the end of the 8-week program period, participants will be asked to mail their device back to appliedVR using a provided, postage-paid mailer.

All outcomes will be assessed at the initial baseline visit and then every 4 weeks for 12 weeks via phone or online questionnaires. A core subset of these outcome measures, mainly pain and use of analgesic medications, will be collected daily during the 8-week program. Patients will be asked to complete a paper or online REDCap diary to track their pain levels, opioid/non-opioid pharmacotherapy, and device use from home. The daily log will capture the NPRS at the same time each evening (\pm 2 hours). Participants will be asked to record their NPRS at least 2 hours after taking any pain medication. Medication use will be recorded in terms of medication type, dose, and time of administration.

Outcomes data also may be collected via REDCap, a secure research electronic data capture system, or OBERD, a software system for patient-reported outcomes already in use at the study clinics. To assess opioid use, the investigators will query Pennsylvania's Prescription Drug Monitoring Program (PDMP) database. To maintain compliance with ABC-MAP Act 191 of 2014, study investigators will query the PDMP only for their existing patients. Patient clinical information will be extracted from their electronic medical records, including patient demographics, medical history and prescription information.

The EaseVRx devices will collect information related to device usage (i.e. frequency and duration of use, features utilized, completion rates). Patients may be contacted via phone or email by the study team to further encourage participation.

Outcome measures include:

- **Program Feasibility:**
 - Patient compliance will be assessed in two ways:
 - Treatment dose (actual minutes of VR or sham use per day); and
 - Treatment duration (actual number of days VR or sham used).
 - Program retention will be evaluated by the number of days that participants completed all outcome assessments.
 - Patient satisfaction will be assessed once at the end of the program by asking the participant four questions to evaluate the program:
 - Please tell me if you agree or disagree with the following statements:
[strongly agree, somewhat agree, somewhat disagree, strongly disagree]
 - The VR headset was easy to use.
 - I enjoyed using the VR headset.
 - The content in the VR headset helped me cope with my chronic pain.
 - Today, on a scale of 1 to 10, where 1 means you would definitely NOT recommend VR treatment and 10 means you WOULD definitely recommend VR treatment, how likely are you to recommend VR treatment to someone else?
 - Patient safety will be assessed by monitoring subjects for the occurrence of adverse events (AE).
- **EaseVRx Efficacy:**

- Pain will be assessed via the standard Geisinger Numerical Pain Rating Scale (NPRS) ranging 0-10 (0 = least amount of pain, 10 = worst amount of pain).
- Pain Coping Skills will be assessed via:
 - Pain Self-Efficacy Questionnaire (PSEQ-2)^{114, 115}, which measures the confidence people with ongoing pain have in performing activities while in pain;
 - Pain Catastrophizing Scale (PCS-4)¹¹⁶, which measures the impact of catastrophizing on the pain experience; and
 - Chronic Pain Acceptance Questionnaire (CPAQ-8)^{117, 118}, which measures the ability to accept and cope with chronic pain.
- Physical function will be assessed using by the Oswestry Disability Index (ODI).
- Analgesic medication use will be assessed in two ways:
 - Extrapolating total milligrams of morphine equivalent doses filled from PDMP database as an indicator of chronic opioid use; and
 - Patient self-reported consumption.
- Quality of life will be assessed using the 12-item Short Form Health Survey (SF-12).
- **Healthcare Cost and Utilization** (*Geisinger Health Plan patients only*):
 - Utilization will be assessed by recording the number of office visits, admissions, emergency room visits, and therapy sessions related to the patient's lower back pain for 12 months. Total milligrams of morphine equivalent doses filled from PDMP database also will be tracked.
 - Cost will be assessed by recording actual total amounts allowed by Geisinger Health Plan (GHP) and paid to the health system, by both insurer and patient, for utilization, medication, and other costs related to the patient's lower back pain.

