4 HYPOTHESIS AND SPECIFIC AIMS

4.1 Primary Aim 1

Compare pain and pain coping skills among the VR sham and the EaseVRx group. *Hypothesis: Chronic low back pain patients randomized to the EaseVRx approach who use the device in accordance with the treatment protocol will have significantly decreased pain scores and improved pain coping skills 4, 8, and 12 weeks after starting the 8-week VR treatment.*

4.2 Secondary Aim 1

Compare physical function as measured by the Oswestry Disability Index (ODI) among the VR sham and EaseVRx group. *Hypothesis: Chronic pain patients randomized to the EaseVRx approach who use the device in accordance with the treatment protocol will have significantly better physical function (i.e. lower ODI scores) 4, 8, and 12 weeks after starting the 8-week VR treatment.*

4.3 Secondary Aim 2

Compare analgesic medication use among the VR sham and EaseVRx group. *Hypothesis: Chronic pain patients randomized to the EaseVRx approach who use the device in accordance with the treatment protocol will have decreased utilization of opioid and non-opioid pharmacotherapy 4, 8, and 12 weeks after starting the 8-week VR treatment.*

4.4 Secondary Aim 3

To assess the feasibility of EaseVRx as a self-administered, home-based approach to chronic pain management, in terms of patient compliance, program retention, patient satisfaction, and safety. *Hypothesis: EaseVRx will be a feasible approach to chronic pain management, with high rates of patient compliance, retention, and satisfaction among chronic pain patients after completing an 8-week course of treatment with EaseVRx.*

4.5 Secondary Aim 4

Compare healthcare cost and utilization among the VR sham and EaseVRx group among patients with Geisinger Health Plan as their primary insurance. *Hypothesis: Chronic pain patients randomized to the EaseVRx approach who use the device in accordance with the treatment protocol will have significantly lower costs and utilization (i.e. office visits, therapy sessions, inpatient/ED admissions) 3 months, 6 months, and 12 months after starting the 8-week VR treatment.*

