6.5.1 Study Time and Events Table

Study Procedures	Day 0 (baseline visit)	Daily for 8 weeks*	4 weeks*	8 weeks*	12 weeks*	6 and 12 months**
Physical examination (office visit)	X					
Review inclusion/exclusion	X					
Demographics, medical history	X					
Informed consent	X					
Randomization	X					
User instructions	X					
NPRS pain score	X	X	X	X	X	
PSEQ-2, PCS-4, CPAQ-8, ODI, SF-12	X		X	X	X	
Program satisfaction questions				X		
Analgesic drug use	X	X	X	X	X	X
Utilization and cost					X	X
Device utilization statistics ¹		X				
AE / Complication Reporting	X	X	X			

¹ EaseVRx and sham VR groups only

* Data collected from patient at home via phone or online; not an in-person visit

** Retrospective review only

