6.7 Secondary Endpoints

Secondary outcome measures include:

- Average daily minutes of VR or sham use at during weeks 1-4 and weeks 1-8.
- Number of days VR or sham used.
- Number of days that participants completed all outcome assessments.
- Patient satisfaction score (min 3 – max 12).
- Likelihood of recommending VR treatment to someone else (min 1 – 10 max).
- Number of adverse events related to the study treatment.
- Change from baseline PSEQ-2, PCS-4, CPAQ-8, SF-12 score at 4, 8, and 12 weeks.
- Change from baseline in total ODI score as well as subscale scores at 4, 8, and 12 weeks.
- Average self-reported daily amount of analgesic medication used during weeks 1-4 and weeks 1-8.
- Total milligrams of morphine equivalent doses filled from PDMP database at 3 months, 6 months, and 12 months.
- Total number of office visits, admissions, emergency room visits, and therapy sessions related to the patient's lower back pain at 3 months, 6 months, and 12 months.
- Total cost of care related to patient's lower back pain at 3 months, 6 months, and 12 months.

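### The retention endpoint is an ambiguous count of fully assessed days that mixes loss to follow-up with missed forms, so it cannot give a retention rate

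*Combined protocol and SAP*

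**What the plan says.** The measure is defined among the feasibility outcomes in Section 6.5 ("Program retention will be evaluated by the number of days that participants completed all outcome assessments") and repeated in Section 6.7 as "Number of days that participants completed all outcome assessments". Neither place gives a range or a window, although the two satisfaction endpoints in the same Section 6.7 list carry a minimum and a maximum.

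Section 6.5 sets two collection schedules. For the full set: "All outcomes will be assessed at the initial baseline visit and then every 4 weeks for 12 weeks via phone or online questionnaires". For the diary items: "A core subset of these outcome measures, mainly pain and use of analgesic medications, will be collected daily during the 8-week program". The time and events table (Section 6.5.1) agrees. The row for "PSEQ-2, PCS-4, CPAQ-8, ODI, SF-12" is marked at Day 0 and at weeks 4, 8 and 12, and not in the daily column. NPRS and analgesic use are marked at those four points and daily as well.

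Secondary Aim 3 (Section 4.4) names retention as one of four components of feasibility, beside compliance, satisfaction and safety. It predicts "high rates of patient compliance, retention, and satisfaction among chronic pain patients" and sets no threshold. Sections 6.1 and 6.8.2 assume a 20% loss, with 126 recruited to leave 100 for analysis.

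**The concern.** Retention asks whether a randomized participant is still in the study at a given time. The plan counts days on which a participant's assessments were complete, and that depends on two things: how long the person stayed and how regularly the forms were filled in while there. The plan already covers adherence to the device separately, through minutes and days of use. Retention is the component that should tell the designers of the larger trial how many participants will be lost.

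Two things are at stake. First, the phrase can be read in ways that put results on very different scales, with maxima of 4 and 56, and two analysts could both claim to have followed the plan. Second, on any of these scales the summary is a mean or median number of days. The aim speaks of a rate, and the recruitment target rests on a proportion lost.

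**Working it through.** **Inputs.** Full-battery occasions: baseline and weeks 4, 8 and 12 (Sections 6.5 and 6.5.1). Diary: daily for 8 weeks, taken here as days 1 to 56. Arm size 63, total 126 (Section 6.2.1). Assumed loss 20% (Sections 6.1 and 6.8.2). The plan states no figure for the retention endpoint, so there is none to reproduce. Its recruitment figure is consistent with its own assumption: 100 / 0.80 = 125, and 126 × 0.80 = 100.8.

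**Range under each reading.**
- Full battery: days 0, 28, 56 and 84, so 4 days, 3 of them after baseline.
- Everything due that day, diary only: 8 × 7 = 56 days.
- The same with the other contacts added: days 28 and 56 already fall inside the diary period, so only day 0 and day 84 are new, giving 56 + 2 = 58.
- Every listed outcome on one day: no such day exists, because satisfaction is asked only at week 8 and utilization and cost are recorded only from week 12. The maximum would be 0, which cannot be intended.

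**Can the count separate staying from leaving?** Write 1 for a complete occasion and 0 for an incomplete one.

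| Reading | Participant who leaves | Participant who stays |
|---|---|---|
| Full battery (weeks 0, 4, 8, 12) | Lost after week 8: 1+1+1+0 = 3 | Missed only week 4: 1+0+1+1 = 3 |
| Diary (days 1–56) | Lost after day 28, all diaries filed until then: 28 | Files every second diary to the end: 56 / 2 = 28 |

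Under the full-battery reading with baseline complete, a participant assessed at week 12 scores 1 + (0 to 2) + 1, so 2 to 4. One not assessed at week 12 scores 1 + (0 to 2), so 1 to 3. The two ranges overlap at 2 and 3.

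A group mean has the same problem. A mean of 3 is compatible with every participant being lost after week 8 (week 12 retention 0%) and with every participant missing only week 4 (week 12 retention 100%).

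On the 58-day scale, week 12 contributes only one day. A participant lost after week 8 with all diaries filed scores 58 − 1 = 57. A participant who reaches week 12 but missed two diaries scores 58 − 2 = 56, which is lower.

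**Precision of a proportion instead.** Half-width of the 95% interval = 1.96 × √(p(1 − p)/n). Taking p = 0.80 for illustration, as the complement of the plan's 20%:
- per arm, n = 63: 1.96 × √(0.16/63) = 0.099, about ±10 points;
- pooled, n = 126: 1.96 × √(0.16/126) = 0.070, about ±7 points.

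**The case against.** A reader might go further and infer that the endpoint can only run from 0 to 4 and so does not measure retention at all. The documents do not support that. The full-battery reading has a textual basis, since Section 6.5 sets the whole outcome set against a daily subset. But the daily items are outcomes too, and a unit of days suits a diary at least as well as four contacts. Taken with complete strictness the phrase gives 0, so even a maximum of 4 needs some allowance for what is due when. That allowance opens the way to 56 or 58. Stating the rule twice in nearly the same words does not settle which is meant. Under each workable reading, someone who leaves early has fewer days on which to score, so the count is related to retention, though impurely.

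Nor does the plan class anyone as retained or not retained, or say that one skipped item makes an assessment incomplete. A reader should not infer that a participant with a full diary and a few blank items would be declared lost.

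It can also be said that this is one secondary feasibility measure with no threshold and no dedicated test, and that week 8 and week 12 proportions could be derived later from data already scheduled. That is correct and limits the weight of the point. It does not remove it. The plan commits to a specific measure that answers its own feasibility question poorly, and choosing a replacement after the data are seen would be a post hoc choice.

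**Conclusion.** The point holds in this form: the retention endpoint is ambiguous (0–4, or 0–56 or 0–58), has no denominator, and under either workable reading combines loss to follow-up with intermittently missed forms. It cannot supply the rate in Secondary Aim 3 or test the 20% loss assumed for recruitment. It does not follow that the count is unrelated to retention.

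The confusion is largest where missed forms are common. If nearly all participants either complete everything or leave for good, the count would track time in study quite well. The documents give no basis for assuming that pattern.

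The precision figures assume 80% retained and all 126 randomized participants in the denominator. The plan states 20% as an overall loss, not as a loss at each contact. The effect is confined to a secondary feasibility endpoint, so the change is worth making but not critical.

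**What to change.** In Sections 6.5 and 6.7, replace the day count with the proportion of randomized participants in each arm who complete the scheduled week 8 contact and, as a separate figure, the week 12 contact, each with a 95% confidence interval. Set these beside the 20% assumption.

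Say what completes a contact, and make clear that the week 8 figure refers to the scheduled contact and not to that day's diary entry, because the events table marks NPRS in both columns. Requiring only the NPRS at that contact, for example, would keep retention apart from questionnaire completeness.

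Report diary completion separately as days filed out of 56, labelled as adherence to assessment.

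The cost is a few sentences in two sections and no new data collection. The downside is one extra feasibility measure to report and a fairly wide interval within each arm.

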6.5.1 Study Time and Events Table

Study Procedures	Day 0 (baseline visit)	Daily for 8 weeks*	4 weeks*	8 weeks*	12 weeks*	6 and 12 months**
Physical examination (office visit)	X					
Review inclusion/exclusion	X					
Demographics, medical history	X					
Informed consent	X					
Randomization	X					
User instructions	X					
NPRS pain score	X	X	X	X	X	
PSEQ-2, PCS-4, CPAQ-8, ODI, SF-12	X		X	X	X	
Program satisfaction questions				X		
Analgesic drug use	X	X	X	X	X	X
Utilization and cost					X	X
Device utilization statistics ¹		X				
AE / Complication Reporting	X	X	X			

¹ EaseVRx and sham VR groups only

* Data collected from patient at home via phone or online; not an in-person visit

** Retrospective review only

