7 SAFETY MONITORING

7.1 Adverse Event Reporting

Clinical adverse events (AEs) will be monitored throughout the study. All AEs will be reported to the institutional review board (IRB) regardless of whether they are considered study related. The date and time of onset and outcome, course, intensity, action taken, and causality to study treatment will be assessed by the study PI. In the event of a serious AE (SAE), this will be reported to the Geisinger IRB (GIRB) according to the GIRB guidelines. All other AEs will be summarized and submitted to GIRB during continuing review.

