7.3 Recording and Reporting

A subject's AEs and SAEs will be recorded and reported from the signing of the informed consent form to the completion of post-treatment outcome measures collection at 3 months.

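### The events table leaves adverse event reporting unmarked at the 8- and 12-week contacts, so weeks 9-12 of the recording window set in section 7.3 have no scheduled ascertainment

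*Combined protocol and SAP*

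**What the plan says.** The events table in section 6.5.1 has a row for "AE / Complication Reporting". It carries marks under Day 0, under "Daily for 8 weeks" and under 4 weeks. The cells for 8 weeks, 12 weeks, and 6 and 12 months are empty.

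Three places in the text describe AE collection more broadly:

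- Section 7.3 sets the recording window for AEs and SAEs: "from the signing of the informed consent form to the completion of post-treatment outcome measures collection at 3 months".
- Section 7.1 states: "Clinical adverse events (AEs) will be monitored throughout the study".
- Section 6.5 says: "All outcomes will be assessed at the initial baseline visit and then every 4 weeks for 12 weeks via phone or online questionnaires". The same section lists patient safety, assessed by AE monitoring, among the outcome measures, without giving an instrument or a timetable for it.

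Safety is one component of Secondary Aim 3 (4.4), and the number of treatment-related AEs is a secondary endpoint (6.7). Section 6.5 also describes a daily "diary to track their pain levels, opioid/non-opioid pharmacotherapy, and device use from home".

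**The concern.** The events table is what study staff normally work from when they prepare each contact. As it stands, it does not prompt them to ask about AEs at the end-of-treatment contact or at the 12-week contact, although section 7.3 expects recording to continue until the 3-month collection is complete.

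All research activity after baseline is remote (6.5), so no later clinic visit exists at which an unprompted event would naturally come to light. The utilization data are a poor substitute. They cover only Geisinger Health Plan members and only care related to low back pain (6.5).

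At stake is the completeness of a safety outcome. A low count of late events can be interpreted only if participants were asked about them.

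**Working it through.** The plan gives no figure to reproduce here. The check compares the schedule with the text and then counts days.

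**Step 1: is the row intact?** The AE row has 7 fields against 7 column headers. Its neighbours fall where the text puts them:

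| Row in 6.5.1 | Marked at |
|---|---|
| NPRS | Day 0, daily, 4, 8 and 12 weeks |
| PSEQ-2, PCS-4, CPAQ-8, ODI, SF-12 | Day 0, 4, 8 and 12 weeks |
| Program satisfaction | 8 weeks |
| AE / complication | Day 0, daily, 4 weeks |

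Satisfaction at 8 weeks agrees with section 6.5, which asks it once at program end. The questionnaires at 4, 8 and 12 weeks agree with section 6.7. The empty AE cells therefore do not look like a fault in reading the table.

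**Step 2: does a daily mark stand in for a contact mark?** Not by the table's own practice. NPRS and analgesic use are marked daily and again at 4, 8 and 12 weeks. AE reporting itself is marked both daily and at 4 weeks. The blank at 8 weeks is thus out of line with the rest of the table, although the daily mark still covers the days up to it.

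**Step 3: length of the required window.** Consent is at Day 0, and the 3-month collection is the 12-week contact, so the window is 12 × 7 = 84 days.

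**Step 4: days covered by the table.** Giving the daily mark full credit, 8 × 7 = 56 days.

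**Step 5: the gap.** 84 − 56 = 28 days, which is weeks 9-12. As a share of the window, 28/84 = 33%, or 4 of 12 weeks. The 12-week contact closes this period. The table uses it for pain, the questionnaires and analgesic use, but not for AEs.

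**The case against.** The strongest reply is that the text already requires what the table omits. Section 7.1 speaks of monitoring throughout the study, section 7.3 fixes the window, and the sentence in 6.5 about four-weekly assessment can be read to include safety. Satisfaction is the visible exception to that sentence, but its exception is stated; none is stated for safety. On this view the gap lies in one table row and not in the protocol as a whole. That is fair, and it limits the point to an internal inconsistency. It does not remove the inconsistency: it means the table conflicts with 6.5 as well as with 7.1 and 7.3.

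A second reply concerns impact, and it largely stands. Devices are mailed back at the end of the 8-week program (6.5). The anticipated reactions are ones that section 7.2 says resolve when the headset is taken off. Weeks 9-12 are therefore off-device, and the schedule is the same in both arms, so the issue is incomplete capture and not a bias between arms.

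A reader might also infer more than the documents support:

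- **That AE reporting stops after week 4, leaving 8 of 12 weeks (67%) uncovered.** This needs the daily mark to be set aside because the sentence describing the diary does not name AEs. But the table explicitly marks AEs in the daily column, and that column is wider than the diary: it also holds device statistics, which the devices log themselves. No diary form is included, so silence in one descriptive sentence does not show that AEs go unasked.
- **That AEs would go unasked at the end of treatment, so the trial could report few or none simply for lack of asking.** The daily mark runs through week 8 and so covers the whole exposure period.
- **That section 7.1 extends AE recording to 12 months.** Section 7.3 gives the specific end point, and the table describes the 6- and 12-month column as retrospective review only.

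**Conclusion.** The point holds as an inconsistency that should be corrected. The AE row in 6.5.1 contradicts section 7.3 and the general statements in 7.1 and 6.5. The firm gap is weeks 9-12: 28 of 84 days, 33% of the required window, including the only scheduled patient contact after treatment.

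This rests on three assumptions: 3 months means the 12-week contact, the window is counted from Day 0, and the daily mark is carried out as shown for all 56 days.

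The consequence is modest. The safety outcome and the count of treatment-related AEs become less complete for the follow-up period. Nothing here shows that events during device use would be missed or that the comparison between arms would be distorted.

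**What to change.** Add marks for AE / complication reporting at 8 weeks and 12 weeks in the table in 6.5.1, so that it agrees with sections 7.1 and 7.3. At those two contacts, ask the same AE question in both arms, covering the time since the previous enquiry.

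Both contacts already take place by phone or online, so no visit is added. The cost is one question per contact, plus investigator assessment and IRB reporting of any additional events, since section 7.1 applies to all AEs whether or not they are related.

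A new daily AE item in the diary is not needed to resolve this. It would add up to 126 × 56 = 7,056 prompts, and the documents do not show that the daily mark lacks a means of collection. The sponsor may still wish to state what that means is.

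### The events table has no adverse-event mark after the 8-week program, although section 7.3 requires recording to 3 months

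*Combined protocol and SAP*

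**What the plan says.** The protocol sets out AE collection in several places.

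- **Events table, 6.5.1.** The row "AE / Complication Reporting" has marks under Day 0, "Daily for 8 weeks" and 4 weeks. The columns for 8 weeks, 12 weeks, and 6 and 12 months are empty. Pain score, the questionnaires and analgesic use are all marked at both 8 and 12 weeks, so those contacts do take place.
- **Section 7.3.** AEs and SAEs are to be "recorded and reported from the signing of the informed consent form to the completion of post-treatment outcome measures collection at 3 months".
- **Section 7.1.** "Clinical adverse events (AEs) will be monitored throughout the study". No schedule is attached.
- **Section 6.5.** "All outcomes will be assessed at the initial baseline visit and then every 4 weeks for 12 weeks via phone or online questionnaires". The outcome list in the same section includes AE monitoring, under program feasibility. The daily diary is described as a means to "track their pain levels, opioid/non-opioid pharmacotherapy, and device use from home"; AEs are not named in it.
- **Section 6.7.** The safety endpoint is "Number of adverse events related to the study treatment", with no time window.

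Section 6.8.1 describes no AE analysis.

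**The concern.** The table and section 7.3 give different end dates for AE collection, and staff who run remote contacts usually work from the table. If they do so here, the last AE enquiry falls at the end of the program, and the four follow-up weeks inside the 7.3 window have none.

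No other source in the plan would clearly fill that gap. After baseline, all research activity is remote. The extraction of clinical information described in 6.5 covers demographics, medical history and prescriptions. The utilization review is limited to Geisinger Health Plan patients and to care for low back pain. An event that began or persisted after week 8 could therefore reach the trial only if the patient volunteered it.

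What is at stake is the reading of the safety data. Safety is one of the components of Secondary Aim 3. With no enquiry, few events in weeks 9-12 could mean that few occurred or that nobody asked, and the data would not show which. The primary endpoint is not affected.

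**Working it through.** **Plan's own figure, used here only for scale.** Section 6.1 gives 126 recruited for 100 completers at 20% dropout. 100 / (1 - 0.20) = 125, and 126 x 0.80 = 100.8. The stated 126 is consistent with this and is even, as 1:1 allocation needs.

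**Reading the row.** The header and the AE row each have seven fields, so they line up:

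| Column | AE mark |
|---|---|
| Day 0 | X |
| Daily for 8 weeks | X |
| 4 weeks | X |
| 8 weeks | none |
| 12 weeks | none |
| 6 and 12 months | none |

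Other rows place single marks sensibly (satisfaction at 8 weeks only). A mark lost when the table was converted to text is unlikely, though it cannot be excluded.

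**Calendar coverage.**
- Window in 7.3: consent to the 3-month collection, taken as the 12-week contact, so 12 weeks.
- Covered by the table: Day 0 plus the daily column, so 8 weeks.
- Not covered: 12 - 8 = 4 weeks, and 4 / 12 = 33%.
- If 3 months is read as 13 calendar weeks: 13 - 8 = 5 weeks, and 5 / 13 = 38%.

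The blank at 8 weeks adds nothing to this, because the daily column already runs to week 8. The calendar gap is weeks 9-12.

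**Patient-weeks in the gap (12-week window).**
- 100 completers: 100 x 4 = 400 of 100 x 12 = 1,200.
- All 126, ignoring dropout: 126 x 4 = 504 of 126 x 12 = 1,512.

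**Share of events falling in the gap.** Let r be the weekly AE rate in weeks 9-12 relative to weeks 1-8. The documents give no value for r, so it is an assumption. With constant rates within each period and equal follow-up, the share is 4r / (8 + 4r):

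| r | Calculation | Share |
|---|---|---|
| 0.05 | 0.2 / 8.2 | 2% |
| 0.10 | 0.4 / 8.4 | 5% |
| 0.25 | 1 / 9 | 11% |
| 0.50 | 2 / 10 | 20% |
| 1.00 | 4 / 12 | 33% |

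This is the share of events that occur where the table schedules no question. It equals the share missed only if none is volunteered or found in another way.

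**The case against.** The strongest reply is that the text already covers week 12 and one table row is the outlier. Section 6.5 puts all outcomes at every 4-week contact to week 12 and counts AE monitoring among the outcome measures; 7.1 and 7.3 point the same way. This largely stands against a reading that a reader might take from the table, namely that the plan as a whole schedules no AE enquiry after week 8. That is true of the table only. It does not remove the contradiction. The 6.5 sentence is loose, since satisfaction is among the listed measures yet is asked once, and no AE question or form is described. If the text governs, the table is wrong and needs the same correction.

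A second reply concerns size. The 6.7 endpoint counts treatment-related AEs only. The headset is mailed back at the end of the program, and 7.2 describes the foreseen effects (motion sickness, vertigo, nausea, vomiting, panic attacks) as remedied by taking it off. Few related events may begin in weeks 9-12, so a low count could be genuine. This stands, and it points to the low end of the range for that endpoint. It carries less weight for 7.3, which is not limited to related events, or for 7.1, which sends all AEs to the IRB whatever their cause.

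A third reply is that the row looks incomplete rather than chosen: it marks week 4, which the daily column already covers, and omits weeks 8 and 12. That is plausible. But a schedule that staff follow has the same effect whether a blank is deliberate or an oversight.

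**Conclusion.** The contradiction is real: the table's AE marks end with the 8-week program, and 7.3 runs to 3 months. If the table is followed, 4 of the 12 weeks (33%) carry no scheduled AE enquiry, about 400 patient-weeks for 100 completers and up to 504 for 126. The share of events affected runs from about 2% to 33% over r = 0.05 to 1, with the low end more likely for treatment-related events. These figures rest on a 12-week window, on staff working from the table rather than the text, and on values of r that the documents do not supply.

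A reader might go further and infer that weeks 9-12 will be presented as fully observed, or that a 12-week AE rate will be understated. The documents do not support that: they specify no AE rate, no exposure denominator and no comparison of program with follow-up weeks. Nor does the missing mark at week 8 open a gap in time. What can be said is that, under the table, a low count in weeks 9-12 would not be interpretable. This merits correction, since it concerns an operating schedule for safety data, but it does not threaten the trial's main result.

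**What to change.** Reconcile the table with 7.3 by marking AE reporting at the 12-week contact, which already takes place by phone or online. A mark at 8 weeks is optional, for consistency with the other rows. Give the AE endpoint in 6.7 the 7.3 window, from consent to the 3-month collection. It would help to add a sentence saying how AEs are asked about at week 12 and in the daily collection, since the diary as described does not mention them.

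The cost is a table edit, a phrase in 6.7 and one AE question at an existing remote contact. No new visit is needed.
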